- After recruitment, participant experiences surgical complications (bladder or bowel injury, etc) that require face-to-face postoperative care
- After recruitment, participant visits the emergency room (ER) for postoperative complaints between surgery and scheduled postoperative visit

Materials and Methods

Study design: Randomized controlled trial.

Once IRB approval is obtained, we will begin recruitment based on the stated inclusion and exclusion criteria. Invitation to participate will be extended to eligible patients by clinic staff with a direct care relationship to the patient during their pre-operative visit in the TTUHSC El Paso Ob-Gyn department. If the patient agrees to participate, research staff will be called in to explain the study in more detail. The patients will be advised that if they agree to enroll, there is a 50% chance their post-operative visit may be via tele-medicine and 50% chance it will be as a traditional visit in the office. They will be asked to fill out a short survey that verifies they have a compatible mobile phone, and will be asked to download the appropriate app. An instruction sheet on how to utilize the tele-medicine application will be given to all patients, to be used in case they are allocated to the tele-medicine group. Once enrolled, surgery will proceed as planned. After surgical stop-time, patients will be allocated to either a traditional postoperative visit group or a tele-medicine postoperative visit via block-randomization, utilizing block sizes of 4:6. This will be achieved by giving patients a sealed envelope that allocates them in a sequential fashion based on a previously generated random series. The envelope will contain information regarding group assignment, along with simple instructions as to how to schedule the post-operative visit within a window between one and three weeks from the surgery.

Both the tele-medicine and traditional visits will be carried out using the same structure.

- 1) Inquire about any concerns the patient has regarding recovery.
- 2) Review findings and procedures done during surgery and pathology results.
- 3) Visually examine abdominal laparoscopic port-sites.
- 4) The opportunity for the patient to ask any additional questions.

In the case of the telemedicine visits, they will open by asking the patient to state her full name, and her date of birth. Additionally, this will be correlated with the code in the instruction sheet in order to verify identity.

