A video-call application that is HIPAA compliant and easily accessible from mobile phones or video-enabled PCs will be used (doxy.me). A Business Associate Agreement between TTUHSC and Doxy.me has been generated in order to comply with HIPAA requirements. Patients will be given a time when they will receive their virtual appointment link, which will be sent to their mobile phone via text. It is expected that patients will use their phone to establish the connection. Providers will utilize a computer station set up with a camera and audio equipment, with a professional appearing backdrop. As part of the consent form, patients will be made aware that they may incur in data charges if they are using a limited data plan, and they are responsible for this expense.

Data will be collected in a de-identified manner. Baseline variables that will be captured include age, ethnicity, BMI, parity, distance from home address to the clinic in miles (calculated using Google maps). Surgery performed and operating time will also be collected. Post-operative visits will be timed. In the case of telemedicine, recorded time will be from when connection is established until disconnection. In the case of the traditional visit, it will be time from when the provider enters the exam room until time the patient exits). Patients will be contacted by phone between 7 to 14 days after the postoperative visit and they will be subjected to a PSQ-18 (Patient satisfaction questionnaire) focused on their post-operative visit, which will be conducted by a member of the research staff blinded to allocation. We will also inspect their medical records to determine if there were any phone calls to the clinic/call-center or visits to the emergency department following the postoperative encounter (within the first 30 days after surgery). In addition to the PSQ-18 questions (after they are completed), patient's will be asked "If they had the opportunity to have switched groups, would they?" and then they will be asked to give an estimate of how much time they utilized in order to complete the postoperative visit including transportation, waiting time, etc. (rounded to the nearest 15 minute increment).

Sample size:

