Our primary outcome is to detect a difference in patient satisfaction. If we expect a 20% relative increase in the experimental arm, assuming two-tailed testing with an alpha of 0.05, and power of 80%, we will need a total sample size of 64 patients. This is considering a base satisfaction score of 70, with a standard deviation of 20.

Safety Procedures:

-Confidentiality and Privacy: Data will be stored in a secure de-identified database. No personal/identifiable information will be collected in this database. A separate list that contains a list of enrolled patients, with information including patient name, phone number and internal research code will also be generated for the purpose of performing the follow-up surveys. The information from the surveys will then be uploaded into the de-identified database by using the internal research code.-Safety – A member of the research staff will be assigned as a safety monitor. Interval analysis will be performed for every 20 patients recruited. If the experimental arm demonstrates an increase of greater than 10% in visits to the emergency-room related to post-operative complaints, or an increase in unexpected complications (wound infection, wound dehiscence, etc.), the study will be halted. However, only patient's undergoing minimally invasive surgery will be included, which is known to have a lower wound-related complication rate than traditional surgery, so we do not expect any significant difference regarding complications.

Data Management:

All data will be collected in a de-identified fashion and stored on Redcap, which is approved TTUHSC IT software. Only approved members of the research team will be granted access. The data will be stored in a secured server. Data will not be linked by code to any identifying information.

Data analysis:

All data analysis will be carried out in SPSS version 24 (IBM, Armonk, NY, USA). We will use T-student to compare demographic variables that are continuous (age, BMI), as well as duration of the visit and number of readmissions or phone-calls. Pearson's Chi Square will be used when analyzing categorical binary variables.

Strengths/limitations

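### Patient-reported time includes travel, and distance to the clinic is already recorded, but the plan neither adjusts this outcome for distance nor names a test for it

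*Combined protocol and SAP*

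**What the plan says.** All references are to the combined protocol and SAP.

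- **Objectives.** The second objective is the difference in time invested by patients and by clinicians.
- **Materials and Methods, data collection.** "Baseline variables that will be captured include age, ethnicity, BMI, parity, distance from home address to the clinic in miles". The type of surgery is also recorded. Allocation happens after surgery ends, so distance from home cannot be affected by it.
- **Materials and Methods, follow-up call.** Patients estimate the time they needed to "complete the postoperative visit including transportation, waiting time, etc", rounded to 15 minutes.
- **Materials and Methods, randomisation.** Allocation is blocked. No stratification factor is named, so the design does not balance distance.
- **Data analysis.** Student's t-test is named for continuous demographics, "as well as duration of the visit and number of readmissions or phone-calls"; Pearson's chi-square is named for binary variables. No regression or covariate appears. No test is named for patient-reported time or for the satisfaction score.

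The visit duration named in Data analysis is the timed encounter, from connection to disconnection or from the provider's entry to the patient's exit. It excludes travel and is a different variable from patient-reported time.

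**The concern.** Travel is a component of patient-reported time by definition, and it applies to the office arm. Differences in distance between patients therefore add scatter to that arm. With about 32 patients per arm and no stratification, a chance imbalance in distance feeds straight into the estimated saving. The measurement that would account for some of this is already on the case report form.

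At stake is the width of the interval around the time saving. There is also a gap to fill in any case: an analysis for this outcome has to be written, and it is better fixed before the data are seen.

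**Working it through.** **1. The plan's own figure.** The Sample size section gives "This is considering a base satisfaction score of 70, with a standard deviation of 20" and a 20% relative increase, so the difference is 0.20 × 70 = 14. With two-sided alpha 0.05 and 80% power:

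n per arm = 2 × [20 × (1.960 + 0.842) / 14]² = 32.04, or 64.07 in total.

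This reproduces "we will need a total sample size of 64 patients" to within rounding (strict rounding up gives 66). At 32 per arm the standard error (SE) is 20 × √(2/32) = 5.00 points. Power is 80.0% by the normal approximation and 78.7% by the t-test. The 64 therefore rests on an unadjusted comparison of satisfaction. The plan gives no precision calculation for patient time.

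**2. What distance can do for patient time.** Let office time be a constant plus b × distance plus other scatter (variance s²). Let telemedicine time not depend on distance (scatter variance t²). Let v be the variance of distance and n the patients per arm. In large samples with 1:1 allocation:

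- unadjusted: SE² = (s² + t² + b²v) / n
- adjusted for distance: SE² = (s² + t² + b²v/2) / n

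Half the travel variance is removed, so the SE can fall by at most about 1 − 1/√2 = 29%. With equal arms, the model with a distance main effect and the model with an arm-by-distance term share this large-sample variance.

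**3. Illustrations.** The inputs are assumptions; none is in the documents. I take n = 32, lognormal distance and t² = 0 (which slightly flatters adjustment). The variance of distance is v = median² × e^(σ²) × (e^(σ²) − 1), where σ is the log-SD, and b is twice the minutes per mile.

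| Median, log-SD | Min per mile each way | Waiting and visit SD (min) | v | b²v | SE before → after (min) | Fall |
|---|---|---|---|---|---|---|
| 8 miles, 0.5 | 1 | 30 | 23.3 | 93 | √(993/32) = 5.57 → √(947/32) = 5.44 | 2% |
| 8 miles, 0.5 | 2 | 20 | 23.3 | 373 | √(773/32) = 4.91 → √(587/32) = 4.28 | 13% |
| 10 miles, 0.8 | 2 | 20 | 170 | 2,720 | √(3,120/32) = 9.87 → √(1,760/32) = 7.42 | 25% |

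**4. Simulation.** 6,000 trials per scenario, 32 per arm, times rounded to 15 minutes, distance plus an arm-by-distance term:

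- 2 min per mile each way: the SE falls by 6-24% (6.69 to 6.27 at the low end, 10.82 to 8.21 at the high end).
- 1 min per mile: it falls by 1-15%.
- No effect of distance: it rises from 5.28 to 5.32, about 1%.

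**5. Which interval is valid.** If distance is centred at the sample mean and multiplied by arm, ordinary robust SEs treat that mean as known. They omit the b²v/(2n) that comes from estimating it. In simulations under assumed inputs, coverage of the population-average saving by a nominal 95% interval was 78-95% in one set and 71-92% in another. A distance main effect with robust SEs, or the interaction with a correction for the estimated mean, covered 93-96% and cut the true SE by about 1-21%.

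**6. The same idea for satisfaction.** Age, distance and a three-level procedure variable use 4 degrees of freedom. At N = 64 the SE is multiplied by √(61/57) = 1.034, so if they explain nothing it goes from 5.00 to 5.17.

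| Variance explained (assumed) | Power with 4 covariate df |
|---|---|
| 0% | 75.9% |
| 5% | 78.0% |
| 10% | 80.1% |
| 20% | 84.5% |

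Against 78.7% unadjusted, break-even is about 7% (4/61 = 6.6% for the SE).

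**The case against.** The strongest reply is that an unadjusted comparison of randomised arms is unbiased and valid, and that this is a self-described pilot in which patient time is not the primary outcome. That stands: omitting distance is a missed opportunity, not a mistake.

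Second, the gain may not matter. In simulations with assumed inputs (45 minutes mean office time excluding travel, 15 minutes for telemedicine), the arm difference was about 66-86 minutes, with median unadjusted t statistics of about 9-13. A narrower interval would not alter that conclusion. The outcome is also recalled 7 to 14 days after the visit and coarsely rounded. This stands too. The benefit lies in how precisely the saving is stated, not in whether one is found.

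Third, a careless adjusted model can be worse than none, as step 5 shows for the interaction term. This stands, and the fix is framed to avoid it.

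Two stronger readings are tempting, and the documents support neither:

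- A reader might infer that adjusting the primary satisfaction score for age, distance and procedure is a free gain in power. The documents give no correlation between any of these and satisfaction, and adjustment loses power if they explain less than about 7% of the variance.
- A reader might infer that the plan prescribes unadjusted t-tests for satisfaction and patient time. The t-test is named for other variables; for these two the plan is silent.

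**Conclusion.** The point holds for patient-reported time only. The outcome includes transportation, distance is recorded and fixed before allocation, and the Data analysis section neither uses it nor names a test. The size depends on travel assumptions that the documents do not supply: a fall in the SE of roughly 1-24% across the scenarios examined (about 1-21% for the models whose intervals also had close to nominal coverage), against a rise of about 1% if distance is irrelevant.

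This is an efficiency improvement. It does not show bias, does not undermine the sample size of 64, and is unlikely to change the direction of the time result. For satisfaction, adjustment is optional and its benefit is unproven.

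**What to change.** In Data analysis, add that patient-reported total time will be compared by linear regression on randomised arm, with distance to the clinic as a baseline covariate and robust (HC3) standard errors. Report the adjusted mean difference with its 95% CI, and keep the unadjusted comparison as a sensitivity analysis.

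If an arm-by-centred-distance term is wanted, because travel applies to the office arm, state that the variance will allow for the estimated mean distance, for example by bootstrapping the whole procedure including the centring.

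Name the primary analysis of the satisfaction score in the same paragraph. If covariates are used there, keep them few, fix them in advance and state the variance they are assumed to explain.

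The cost is a few lines of text and one degree of freedom for distance. No new data, visits or patients are needed.

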Project title: Utilizing telemedicine for delivery of postoperative care following minimally-invasive gynecologic surgery: A randomized controlled trial

Principal Investigator: [name] MD FACOG

Co-Investigators: [name] MD

Research Associate: [name]

Biostatistician: [name]., Professor

Affiliations: Texas Tech University Health Science Center El Paso, Paul L. Foster School of Medicine

Background:

The wide-spread use of minimally invasive techniques in gynecologic surgery has brought several tangible benefits to patients including faster-recovery times, shorter hospital stays, decreased risk of long term complications, to name a few.¹⁻³ Technological advances such as the development of robotic assistance have allowed to further expand the number of cases that can be performed via a minimally invasive approach.⁴ The shift has been such that the landscape regarding operative routes in gynecologic surgery has completely reversed, with now the majority of cases being performed laparoscopically.⁵ Although much has changed intraoperatively, the surrounding structure of an operative has lagged. Specifically, preoperative and post-operative visits are still conducted in a similar way than how it was done 20 years ago. Despite leaps in technology, the field of gynecologic surgery has been slow to widely implement these advances into perioperative practice. One of the specific areas of opportunity is the postoperative visit. It is common practice in the majority of fields to have a visit with the patient approximately 2 weeks after surgery. The objective of this visit is to evaluate how the patient has been progressing, examine the wound site(s), and discuss pathology results from any specimens that were removed during the procedure.

The logistics of this visit involve blocking a time-slot in an established clinic day. Patient is required to transport herself to the clinic site. Once checked-in, there may be a waiting period before being placed in a room for the practitioner to conduct the visit. Once the visit is started, as long as there are no issues, the duration of the interaction may range on average between 3-7 minutes.

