Despite these visits being short and usually straight-forward, the invested time that patients have to dedicate is substantially greater than the actual interaction with the clinician. Furthermore, because of the advantages of minimally invasive surgery, many patients have already returned to work by the time of the postoperative visit which may result in a disruption of their daily work schedule.

The ubiquitousness of high-speed internet and mobile phones have allowed for the field of tele-medicine to thrive in recent years.^{6,7} Although wide-spread application of this modality has not been implemented in the field of gynecologic surgery, other areas such as urology and pediatrics have successfully implemented tele-medicine programs, specifically for postoperative patients, yielding promising results.^{8,9}

We propose a pilot project in which enrolled patients undergoing major gynecologic surgery will be randomized to either a traditional office postoperative visit or a telemedicine postoperative visit. The two groups will then be compared on a variety of metrics including clinical outcomes, patient satisfaction and time.

Objectives

1. Determine if there are differences in patient satisfaction between traditional postoperative visits and telemedicine postoperative visits
2. Determine the difference in time invested from the patient's side and clinicians side in order to complete the postoperative visit interaction
3. Analyze if there is a difference between groups regarding visits to the emergency department related to the surgery, delayed postoperative complications, etc.

Hypothesis

Patient satisfaction will be greater in the tele-medicine group.

Total time invested will be decreased.

There will be no difference in visits to the emergency department or unrecognized postoperative complications

Inclusion criteria

Female patients between ages 18-60

Have access to smart-phone with video /audio and internet capabilities

Undergoing laparoscopic gynecologic surgery that requires a postoperative visit

- Total laparoscopic hysterectomy
- Laparoscopic removal of adnexal structures
- Laparoscopic excision of endometriosis

Exclusion criteria

Patient unwilling to participate

Patient unwilling to install and utilize the telemedicine app on their smart phone.

Recruited participants will be deemed ineligible to continue the study if:

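### Timed visit duration is the only measure of clinician time, but it records encounter length with end points that differ between arms, in ways that can make video look shorter

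*Combined protocol and SAP*

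**What the plan says.** The Objectives section sets the target: "Determine the difference in time invested from the patient's side and clinicians side in order to complete the postoperative visit interaction". The Hypothesis section gives the expected direction: "Total time invested will be decreased".

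The Materials and Methods section defines one clock per arm. For telemedicine, "recorded time will be from when connection is established until disconnection". For the traditional visit, "it will be time from when the provider enters the exam room until time the patient exits". No other clinician-side time is collected.

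Patient-side time comes from a later telephone call, in which she is asked to "give an estimate of how much time they utilized in order to complete the postoperative visit including transportation, waiting time, etc", rounded to 15 minutes.

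On the video process, the same section says that the link is texted to the patient's phone and that providers work from an equipped computer station. It has no rule for failed connection attempts or dropped calls. The Background says the interaction, when there are no issues, "may range on average between 3-7 minutes". The Data analysis section assigns a Student t-test to visit duration.

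**The concern.** The quantity in objective 2 is clinician time invested to complete the visit. The quantity recorded is the length of the encounter. The gap between the two need not be the same in both arms.

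- **Start.** The video clock starts at connection. If the clinician opens the session, waits for the link to be used or repeats a failed attempt, that work comes before the clock and is not recorded.
- **End.** The office clock stops when the patient leaves the room, which can be after the clinician has finished. The video clock has no such tail.

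The first feature can understate the video figure and the second can overstate the office figure. At stake is whether a difference in the duration t-test can be read as a saving of clinician time, or only as a difference in what was timed.

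**Working it through.** **1. The clocks side by side** (Materials and Methods)

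| | Video | Office |
|---|---|---|
| Clock starts | connection made | provider enters room |
| Clinician time before the start | opening session, connecting, failed attempts: not recorded | going to the room, any wait: not recorded |
| Clock stops | disconnection | patient leaves the room |
| Time after the clinician is free | none | counted, if the patient leaves later |

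The mismatch at the end is written into the definitions. At the start, both clocks leave out whatever comes before the encounter. An imbalance there depends on connecting taking the clinician longer than going to a room. That is plausible, but the documents give no figure for it.

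**2. Can another measure recover the missing time?** No. The telephone estimate is the patient's own time, rounded to 15 minutes. That rounding unit is more than twice the longest stated interaction of 7 minutes.

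**3. Dropped calls.** Take a hypothetical call with 6 connected minutes that drops at minute 2 and resumes after a 1-minute gap (assumption). The recorded time is 2 minutes if the clock stops at the first disconnection, 2 + 4 = 6 if connected segments are summed, and 6 + 1 = 7 if it runs to the final disconnection. The text does not choose between these.

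**4. Scale.** Let w be the net minutes by which the timing rules alone shorten video relative to office. Against 3 to 7 minutes, w = 1 is 1/7 = 14% to 1/3 = 33%, and w = 2 is 2/7 = 29% to 2/3 = 67%.

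**5. Illustration for the t-test.** The plan states no figure for the time outcome, so there is none to reproduce. Assume the planned 64 patients split 32 per arm, equal true clinician time, two-sided alpha 0.05, and an SD of 1, 2 or 3 minutes. The non-centrality is (w/SD) × √(32/2) = 4w/SD on 62 degrees of freedom. The chance of a significant result is then:

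| w (min) | SD 1 | SD 2 | SD 3 |
|---|---|---|---|
| 1 | 0.98 | 0.50 | 0.26 |
| 2 | over 0.99 | 0.98 | 0.75 |

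With no timing artefact, every cell would be 0.05. Both w and the SD are assumed, so the table shows sensitivity and does not estimate the bias.

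**The case against.** The strongest reply is that the two start points are parallel: each clock begins when patient and provider meet, and each omits what went before. This stands. A reader might infer that the omitted minutes occur only in the video arm, because the Background describes the office patient being roomed before the practitioner arrives. That passage concerns the patient's wait. It does not say that clinicians never wait in the office, and nothing says that they sit idle at the video station.

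A reader might also infer that time lost to a dropped call goes uncounted. That depends on one reading of the stop point; if the clock runs to the final disconnection, the gap is counted. What the documents support is that a rule is missing.

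A further point is that the identity check in the video visit (name, date of birth, code) falls inside the video clock and lengthens it. This is true, but the check is real clinician work and is properly counted. It does not make up for work left out.

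Finally, the trial calls itself a pilot, and this is one component of a secondary objective. That limits the weight of the point. It does not answer the mismatch between patient exit and disconnection, which needs no assumption about waiting.

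**Conclusion.** The point holds in a limited form. The timed visit is the only measure of the clinician time named in objective 2. It captures encounter length, its end points differ between arms, and it leaves out clinician effort in establishing the video connection. Both features can make recorded video time shorter relative to office time. Whether they do, and by how much, cannot be estimated from the documents: connection time, the delay before the patient exits and the SD of duration are all absent. The illustration shows only that a minute or two could matter against a 3 to 7 minute interaction.

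A reader might take this to undermine the whole hypothesis of reduced total time. The documents do not support that: patient-side time is collected separately and its question covers travel and waiting. The primary outcome, satisfaction, and its sample size of 64 are untouched.

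**What to change.** In the timing paragraph of the Materials and Methods, define clinician time in the same way for both arms:

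- **Start:** when the clinician turns to that patient's visit, by opening the session and beginning to connect, or by going to the exam room.
- **Stop:** when the clinician is free, at the final disconnection or on leaving the room.
- **Include** failed connection attempts and reconnection gaps.
- **Late patients:** state one rule for waits and apply it in both arms.

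Make this the clinician-time outcome for objective 2 and name it in the Data analysis section. Report the encounter duration as now defined separately, so that a shorter conversation can be told apart from less clinician time. Changing the video clock alone would not do: a late patient would then count against video but not against office, and the mismatch at the end would remain.

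The cost is a few extra timestamps per visit and a telemedicine figure that may be less favourable. The definition should be in place before visits are timed, because unrecorded intervals cannot be recovered afterwards.

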This is an innovative study that seeks to apply existing and well established technology to improve patient experience in regards to the postoperative portion of their care. If found to be effective, it could also have the potential of reducing costs for the patient and clinic. The study is strong given its randomized nature. Randomization will occur after the surgical procedure is completed to avoid bias that could affect intra-operative technique or decisions. We will also use validated instruments to assess patient satisfaction.

The main limitation of the study is that patients and providers who are doing the post-operative visit cannot be blinded. This may lead to some degree of subconscious bias in the way the visits (traditional or tele-medicine) are carried out, which could potentially impact duration and patient satisfaction. We will attempt to mitigate this by utilizing a standardized visit structure which is exemplified in the methods section. Additionally, the research staff that will conduct the survey will be blinded to allocation. Patients will be instructed during the consenting process to avoid revealing their group when the surveyor calls.

Timeline

Accrual will commence after IRB approval. We expect to enroll on average 4 patients per week.

References

2. ACOG Committee Opinion No. 444: choosing the route of hysterectomy for benign disease. *Obstet Gynecol*. 2009;114(5):1156-1158.
7. Gutierrez G. Medicare, the Internet, and the future of telemedicine. *Crit Care Med*. 2001;29(8 Suppl):N144-150.

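### The office visit clock stops when the patient exits, so the only planned measure of clinician time can include time after the clinician has left, in the office arm only

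*Combined protocol and SAP*

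**What the plan says.** Objective 2 asks for the difference in time invested from the patient's side and from the "clinicians side in order to complete the postoperative visit interaction". The matching hypothesis is "Total time invested will be decreased".

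Materials and Methods plans two time measures. One is the patient's own estimate, given by telephone to the nearest 15 minutes and covering travel and waiting. The other is a timed visit. For telemedicine, "recorded time will be from when connection is established until disconnection". For the office visit, "it will be time from when the provider enters the exam room until time the patient exits".

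Data analysis applies the t-test to continuous demographic variables, "as well as duration of the visit and number of readmissions or phone-calls". Strengths/limitations accepts that unblinded conduct could affect visit duration and answers: "We will attempt to mitigate this by utilizing a standardized visit structure". The Background puts the usual clinician interaction at 3 to 7 minutes.

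**The concern.** The office interval opens on a clinician event and closes on a patient event. The telemedicine interval closes on one event that ends the encounter for both. No provider exit time is recorded in the office, and nothing in the plan requires the provider to stay until the patient leaves. If the provider goes first, the remaining minutes are booked to the office visit although no clinician time is being spent.

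The patient's recalled total covers the patient's side only, so the timed visit carries the clinician half of Objective 2 alone. The possible error runs the same way as the time hypothesis. It also runs the same way as the remark in Strengths/limitations that, if effective, "it could also have the potential of reducing costs for the patient and clinic", although that remark is conditional and is not tied to visit minutes. A systematic offset is not averaged away by more patients, and a common visit structure does not align the stop events. The interaction is short, so even a small lag is a noticeable share of what is measured.

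**Working it through.** **1. The two clocks side by side.**

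| | Start | Stop |
|---|---|---|
| Office | provider enters | patient exits |
| Telemedicine | connection established | disconnection |

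**2. Sign of the stop-rule component.** Let V be the time the provider leaves and P the time the patient exits. Contact ends at the earlier of the two, so the recorded office time exceeds contact time by L = max(0, P − V). If the provider leaves first, L is positive. If they leave together or the patient leaves first, L is zero. It cannot be negative. Disconnection leaves no equivalent interval in the telemedicine arm.

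**3. Sign of the whole measure.** The telemedicine start rule does not say who must be present. Let A ≥ 0 be time connected before the clinician begins. Then

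recorded difference (office − telemedicine) = true difference + mean L − mean A.

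The documents give neither L nor A, so the net sign is not determined. The identity check that opens the telemedicine visit is real clinician work; it belongs in the true difference, not in A.

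**4. The plan's own sample size.** Inputs from Sample size: base score 70, 20% relative increase (0.20 × 70 = 14 points), SD 20, two-sided alpha 0.05, power 80%. Per arm, n = 2 × (1.960 + 0.842)² × 20²/14² = 32.04, which rounds up to 33 (66 in total). The stated 64 is 32 per arm, with power 79.96% by the normal approximation, so the figure reproduces to within rounding. It rests on satisfaction and does not depend on visit timing. It is used here only to supply 32 per arm.

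**5. What a lag would do to the t-test (illustration).** Assume no true difference, A = 0 and a constant lag b added to every office visit. The lag and the SD of duration are both assumptions. The test has 2 × 32 − 2 = 62 degrees of freedom and noncentrality b / (SD × √(2/32)) = 4b/SD. Two-sided rejection rates from the noncentral t:

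| Lag b | SD 2 min | SD 3 min | SD 4 min |
|---|---|---|---|
| 0 | 5% | 5% | 5% |
| 0.5 min | 4b/SD = 1.00: 16.6% | 0.67: 10.1% | 0.50: 7.8% |
| 1 min | 2.00: 50.4% | 1.33: 25.9% | 1.00: 16.6% |

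The rate reaches 10% at a lag of 0.33 minute (about 20 seconds) for SD 2 and 0.50 minute (30 seconds) for SD 3. Letting the lag vary between patients (exponential, same means, added to gamma durations with mean 5 minutes; 40,000 runs) changes little: 16.5% and 9.9% at 0.5 minute, 46.5% and 25.4% at 1 minute, for SD 2 and 3.

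Against the 3 to 7 minutes in the Background, 0.5 minute is 0.5/7 to 0.5/3, or 7% to 17%, and 1 minute is 14% to 33%.

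**The case against.** The protocol calls the variable the duration of the visit, not clinician time. As a visit duration, patient exit and disconnection are both reasonable end points. This is fair, but Objective 2 names the clinician's side and no other planned measure can serve it.

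Nothing in the documents shows that the lag occurs. The four-step visit ends with the patient's questions and lists no later task that would keep her in the room. This stands: the component is possible, not demonstrated, and may be zero.

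The size is wholly assumed. The 50% rate needs both a full 1-minute lag and the smallest SD; at SD 4 it is 17%. This also stands. The table shows sensitivity to a lag and does not estimate this trial's error rate.

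A reader might go further and infer that the time comparison as a whole is biased towards telemedicine. The documents do not support that. Time connected before the clinician starts, or spent fixing sound or picture after connecting, would lengthen the telemedicine arm.

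A reader might also count clinician waiting before the call as a second effect in telemedicine's favour, since "Patients will be given a time when they will receive their virtual appointment link" and the connection must then be made. But an office provider's wait before entering the room is equally uncounted, so the documents do not establish a one-sided effect.

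**Conclusion.** The point holds as a narrow defect of definition. The office stop rule can add time that is not clinician time, and it can do so in the office arm only; that component is zero or favours telemedicine. Its size is unknown, and the net direction of the measure as a whole is not established.

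Under the assumptions in the working (32 timed visits per arm, no true difference, equal SDs of 2 to 4 minutes), a half-minute lag would raise the chance of a significant result from 5% to between 8% and 17%, and a one-minute lag to between 17% and 50%. The scope is the clinician half of one secondary objective in a trial that the protocol describes as a pilot. The satisfaction outcome, the sample size of 64 and the patient's recalled total time are unaffected. This is a low-priority change, worth considering because it is cheap.

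**What to change.** For clinician time, stop the office clock when the provider leaves the room or contact ends, whichever is first. Time telemedicine from when clinician and patient are both connected until disconnection, with the identity check included. Patient exit may be kept as a separate room-occupancy time. Compare the two contact times by arm with the planned test.

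If provider waiting is also of interest, record in both arms when the provider is ready, and add the waiting to both. Adding it to telemedicine alone would create an imbalance in the other direction; otherwise leave waiting out.

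The core change costs one altered stop point and, at most, one extra time on the data form. The optional waiting analysis would add a provider-ready time in each arm. Randomization, sample size and the primary outcome do not change. The change has to be made before visits are timed, because without a recorded provider exit the interval after contact cannot be separated out later.
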